#### 10.1.2 Secondary Endpoints

Insulin usage will be estimated from the one-week self report values. Estimates of population means and confidence intervals for those means will be reported for each follow-up visit. Linear mixed models methods will be used to describe the profile of change with time.

Numbers of severe hypoglycemic events will be estimated from the self report values obtained at each follow-up visit. Estimates of population means and confidence intervals for those means will be reported for each follow-up visit. Linear mixed models methods with appropriate likelihood functions will be used to describe trends with time.

HbA1c and serum creatinine levels will be measured at central laboratories at study entry and at the annual follow-up visit. GFR will be estimated using the updated CKD-EPI method. Estimates of population means and confidence intervals for those means will be reported for each follow-up visit. Linear mixed models methods will be used to describe trends with time.

Incidence of serious adverse experiences will be tabulated by body system and MedRA code. Life table methods will be used to estimate mortality rates.

The overall incidence of alloantibody conversion will be reported as a rate per 100 days of follow-up. A 95% confidence interval for the rate will be computed using boot-strap methods.

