## 1. BACKGROUND AND RATIONALE

### 1.1 Background

The Clinical Islet Transplant Consortium opened in October 2004 under a research initiative (RFA-DK-04-005) sponsored by the National Institute of Diabetes and Digestive and Kidney Diseases (NIDDK) and the National Institute of Allergy and Infectious Diseases (NIAID). This consortium conducts seven trials in islet transplantation, six of which (CIT02, CIT03, CIT04, CIT05, CIT06, and CIT07) will be the source of study subjects in CIT08. Approximately 75 subjects are expected to be enrolled and followed in this trial.

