#### 4.1.2 Secondary Endpoints

Secondary endpoints include the following:

- Serum creatinine and calculated eGFR at each annual study visit
- Incidence of serious adverse events during the 12-month period preceding each annual study visit
- Insulin requirements during a one-week period preceding each annual study visit
- Incidence of severe hypoglycemic events during the 12-month period preceding each annual study visit
- HbA1c levels at each annual study visit
- All causes of mortality
- Presence of alloantibody after graft failure, in the absence of immunosuppression

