### 7.2 Follow-up Visits

Subjects will be followed in this study after termination from the CIT parent study until the end date of the CIT08 study. Follow-up is comprised of quarterly visits done locally for safety monitoring and annual visits at the study center to assess graft function (if applicable) and safety.

Retrospective medical chart review will be conducted as needed to collect available follow-up information due to:

- delayed enrollment in CIT08 after termination from the CIT parent study
- the time period between termination from CIT08 prior to extension of the duration of follow-up and subsequent re-enrollment

This retrospective chart review will collect evidence of graft failure in addition to the follow-up assessments outlined in Appendix 1.

Subjects are allowed to concurrently enroll in and be screened for a non-CIT islet transplant study at any point during participation. Once study treatment in the non-CIT study is initiated, they will be withdrawn from CIT08 (see section 6.1).

Subjects with confirmed **graft failure** will not complete metabolic assessments. Subjects who experience graft failure and subsequently stop immunosuppression will have alloantibody assessed 3 months after their last dose of immunosuppression.

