### 9.2.1 Immune Assays

#### 9.2.1.1 ALLOANTIBODY

Development of alloantibody is generally associated with longer term graft loss. Development of alloantibody specific for 1 or 2 HLA antigens can now be defined using assays that incorporate HLA specific monoclonal antibodies. Alloantibody assessments will be performed at each site's laboratory for subjects who experience graft failure during participation in CIT08 and subsequently discontinue immunosuppression.

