## Appendix 1. Schedule of Events for Extended Follow-up

Visit schedule based on anniversary of last islet transplant in CIT parent study; visit schedule repeats each year.	Timing	SC	Local Visits 			On-Site Visit
			3 month	6 month	9 month	Anniversary of Final Islet Transplant
	Visit #	0	See MOP for Table of Visit Numbers			
Visit Window (specified in days)		- 90	±14	±14	±14	± 30
GENERAL ASSESSMENTS						
Informed Consent		X				
Evaluate Inclusion/Exclusion Criteria		X				
Physical Exam		X 				X
AE /Hypoglycemic Events/Toxicity Assessment 		X 	X	X	X	X
Calculated GFR		X 				X
Insulin use		X 	X	X	X	X 
Urine pregnancy test (females)		X				
LOCAL LABORATORY ASSESSMENTS						
CBC (WBC + Diff & Plat) 		X 	X	X	X	X
Chemistry 		X 	X	X	X	X
Lipids 		X 				X
Alloantibody		Collect 3 months after immunosuppressive medication is stopped following graft failure.				
CENTRAL LABORATORY/METABOLIC ASSESSMENTS						
HbA1c 		X 				X
Fasting serum gluc/c-pep & serum creatinine 		X 				X
MMTT 		X 				X
CARDIOVASCULAR ASSESSMENTS						
Carotid intimal thickness (IMT)		Collect at 5 years post-initial-islet transplant visit in subjects who completed the baseline carotid IMT assessment in their CIT parent study. 				
IMMUNOSUPPRESSION LEVELS						
Blood Trough Levels (if applicable) 		X 	X	X	X	X
Visit schedule based on anniversary of last islet transplant in CIT parent study; visit schedule repeats each year.	Timing	SC	Local Visits 			On-Site Visit
			3 month	6 month	9 month	Anniversary of Final Islet Transplant
	Visit #	0	See MOP for Table of Visit Numbers			
Visit Window (specified in days)		- 90	±14	±14	±14	± 30
MECHANISTIC ASSAYS - University of Pennsylvania Sub-Study Only						
Autoantibody 				X		X
Immunophenotyping 				X		X
Cytokine profiling 				X		X
Glucose-potentiated arginine 						X
ARCHIVED SAMPLES						
Serum						X

---

 These visits are performed locally but can be done on site if preferred.

 Only collect if screening is  $\geq 90$  days since final parent study visit. Otherwise, results from final parent study visit should be used for screening (Visit 0).

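### CIT08 plans an alloantibody conversion rate per 100 days, which fits neither the endpoint nor the single test taken after graft failure, so the figure cannot be interpreted

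*Protocol*

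**What the plan says.** The file holds two protocols: CIT04 and its long-term follow-up study, CIT08. This point concerns CIT08.

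- **Endpoint (CIT08 4.1.2):** "Presence of alloantibody after graft failure, in the absence of immunosuppression". This is a yes/no state in a defined subgroup.
- **Who is tested, and where (CIT08 9.2.1.1):** "Alloantibody assessments will be performed at each site's laboratory for subjects who experience graft failure during participation in CIT08" and who then stop immunosuppression.
- **When (CIT08 7.2):** "Subjects who experience graft failure and subsequently stop immunosuppression will have alloantibody assessed 3 months after their last dose of immunosuppression".
- **Schedule (CIT08 Appendix 1):** the alloantibody row reads "Collect 3 months after immunosuppressive medication is stopped following graft failure". Nothing is scheduled at screening or at the quarterly or anniversary visits.
- **Analysis (CIT08 10.1.2):** "The overall incidence of alloantibody conversion will be reported as a rate per 100 days of follow-up", followed by "A 95% confidence interval for the rate will be computed using boot-strap methods".

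Section 10.1.2 defines neither conversion nor the follow-up that counts.

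**The concern.** Three things change between the endpoint and its analysis. Presence becomes conversion, a subgroup becomes the overall incidence, and a status at one time becomes a person-time rate. The sampling supports only the first member of each pair.

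The result matters because sensitization is a recognised harm of a failed islet graft. CIT04 section 1.5.1.3 says that high panel-reactive antibody levels may lengthen a later wait for a kidney. It puts elevated levels (above 20%) at about 84% of recipients who had lost function and stopped immunosuppression. It also gives about 25% of islet-alone recipients while still on immunosuppression, so a single positive sample after stopping is not necessarily a new conversion.

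A reader of the CIT08 report needs to know how many of the tested subjects were positive. Section 10.1.2 as written does not ask for that number.

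**Working it through.** CIT08 states no expected alloantibody rate, so there is no figure of its own to reproduce. The check asks what the planned measure returns for fixed antibody results.

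**Inputs**
- Cohort: 75 (CIT08 1.1: "Approximately 75 subjects are expected to be enrolled and followed in this trial").
- Assumed, because the documents do not give them: 10 subjects tested, 8 positive, mean follow-up 2 to 5 years.
- Time from stopping to sampling: 3 months, taken as 90 days.

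**Rate if all follow-up counts:** 100 × positives / (75 × 365.25 × years)
- 2 years: 800 / 54,787.5 = 0.0146 per 100 days
- 3 years: 800 / 82,181.25 = 0.0097
- 5 years: 800 / 136,968.75 = 0.0058

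**Rate if only the days from stopping to sampling count:** 100 × 8 / (10 × 90) = 0.89 per 100 days.

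**Proportion among those tested:** 8/10 = 80%, Clopper-Pearson 95% CI 44.4% to 97.5%. CIT04 Table 5 gives the same interval for 8 of 10 (0.4439 to 0.9748).

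The antibody results are identical in every line. The all-follow-up rate moves by 5/2 = 2.5-fold with mean follow-up alone, most of which comes from subjects who are never tested. Switching the denominator moves it by 0.889/0.0146, about 61-fold, at 2 years and by 0.889/0.0058, about 150-fold, at 5 years.

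**Wider range.** Let 84% of those tested be positive, let f be the share of the cohort tested and d the mean follow-up in days. The cohort size cancels and the all-follow-up rate is 84f/d. The longest possible window, from June 2011 (activation) to 1 July 2017, is 2,222 days counted from 1 June.

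| Share tested (assumed) | Mean follow-up, days (assumed) | Rate per 100 days |
|---|---|---|
| 10% | 2,222 | 0.0038 |
| 20% | 2,222 | 0.0076 |
| 20% | 1,095 | 0.0153 |
| 20% | 365 | 0.046 |
| 40% | 365 | 0.092 |

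On the 90-day denominator the rate is 84/90 = 0.93 whatever the share tested.

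**Does the bootstrap help?** With 15 tested and 13 positive (assumed), 75 subjects and 1,095 days each, the rate is 100 × 13 / 82,125 = 0.0158, with a subject-bootstrap 95% interval of 0.0085 to 0.0244. The proportion is 86.7% (exact 95% CI 59.5% to 98.3%). The bootstrap reflects sampling variation around the rate. It does not settle which days belong in the denominator or when conversion happened.

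**The case against.** A reader might infer that neither conversion nor a rate can be derived. The documents do not support that. A crude rate can be computed, as above. Conversion cannot be derived from CIT08 samples alone, but it could be approximated for subjects from CIT04. That protocol excludes patients with anti-HLA antibodies above background (3.2, criterion 8), tests in a central laboratory (9.2.1.2) and samples repeatedly (Appendices 1 to 5). CIT08 simply does not name such a result as its reference. The other five parent protocols are not shown, so nothing can be said about them.

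A reader might also infer that heavy sensitization will look negligible. That depends on counting everyone's follow-up. The word overall makes this reading plausible, but 10.1.2 does not fix it, and a 90-day denominator gives about 0.9 per 100 days.

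The illustration rests on assumed counts and follow-up. The 84% is quoted without a time point and refers to levels above 20%, while CIT08 sets no positivity threshold for its local test, so carrying it over is an extrapolation.

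The consequence is limited too. This is the last of seven secondary endpoints in 4.1.2 and is absent from the CIT08 synopsis. CIT08 is a single-arm cohort with no stopping rules. CIT04's own sensitization endpoint, with its central sampling, is unaffected.

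Finally, person-time definitions are often left to a statistical analysis plan. That would answer a silence. Here the protocol has already fixed the measure, the unit and the interval method, and they do not fit its endpoint or its sampling.

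**Conclusion.** The point holds as a mismatch between a stated analysis and its own endpoint and schedule, and it should be corrected. The rate in 10.1.2 can be calculated but not interpreted, for four reasons: the conversion date is unobserved, no reference sample is named, untested subjects contribute days but no possible event and are not known to be negative, and the person-time is undefined.

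On the assumed 8 of 10 positive in a cohort of 75, the same results give 0.015 or 0.006 per 100 days (mean follow-up 2 or 5 years), or about 0.9, according to whose days are counted. The proportion is 80% (44% to 97%) in every case. The size of the discrepancy depends on the assumed counts and follow-up; the mismatch itself does not.

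**What to change.** In CIT08 10.1.2, replace the alloantibody sentences with the following:

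- the proportion alloantibody-positive 3 months after stopping immunosuppression among subjects tested, with an exact binomial 95% CI;
- the number eligible for the test but not tested;
- where a parent-study alloantibody result exists, positives split into already positive and newly positive against the last such result, with a note that the parent assay was central (shown for CIT04) and the CIT08 assay is local.

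Drop the per-100-day rate and its bootstrap interval.

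The cost is a short text change in 10.1.2, carried into the statistical analysis plan through the amendment route in CIT08 10.3. No new samples or visits are needed.

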### 10.2 Patient and Demographic Data

#### 10.2.1 Baseline Characteristics and Demographics

Summary descriptive statistics for baseline and demographic characteristics will be provided for all subjects in the ITT sample. Demographic data will include age, race, sex, body weight, and height; these data will be presented in the following manner:

- Continuous data (*i.e.*, age, body weight, and height) will be summarized descriptively by mean, standard deviation, median, and range.
- Categorical data (*i.e.*, sex and race) will be presented as enumerations and percentages.

Statistical presentation for baseline and demographic characteristics may be further summarized by values of important baseline predictors of outcome and will be further defined in the SAP.

### **10.3 Reporting Deviations from Original Statistical Plan**

The principal features of the study design and of the plan for statistical analysis of the data are outlined in this protocol and in the subsequent SAP. Any changes in these principal features will require a protocol or an SAP amendment, which would be subject to review by the independent DSMB, the study sponsor, and the health authorities. These changes will be described in the final report as appropriate.

## **11. IDENTIFICATION AND ACCESS TO SOURCE DATA**

### **11.1 Identifying Source Data**

The investigator is required to keep accurate records to ensure that the conduct of the study is fully documented (see section 12). The results of all clinical and clinical laboratory evaluations will be maintained in the subject's medical records and the data will be transferred to clinical CRFs.

Safety data will be recorded on CRFs specifically designed for this purpose. All data will be reviewed periodically by the DSMB and IRB. The DSMB and/or the IRB have the authority to withdraw any subjects and/or terminate the study because of safety findings.

### **11.2 Permitting Access to Source Data**

The investigational site participating in this study will maintain the highest degree of confidentiality permitted for the clinical and research information obtained from the subjects in this clinical trial. Medical and research records should be maintained at each site in the strictest confidence. However, as a part of the quality assurance and legal responsibilities of an investigation, the investigational site must permit authorized representatives of the sponsor(s), including pharmaceutical collaborators and their commercial partners, and health authorities to examine (and when required by applicable law, to copy) clinical records for the purpose of quality assurance reviews, audits, and evaluations of the study safety and progress. Unless required by the laws that permit copying of records, only the coded identity associated with documents or with other subject data may be copied (and all personally identifying information must be obscured). Authorized representatives as noted above are bound to maintain the strict confidentiality of medical and research information that is linked to identified individuals. The investigational site will normally be notified before auditing visits occur.

## 12. QUALITY CONTROL AND QUALITY ASSURANCE

Site monitoring will be conducted to ensure that human subject protection, study procedures, lab procedures, study intervention administration are performed to comply with pertinent regulations, sponsor requirements, and GCP/ICH guidelines, and in accordance with the site and sponsor SOPs. DAIT, NIAID, or a designee will conduct site monitoring visits related to the protocol procedures and GCP standards.

### 12.1 Compliance, Access, Entry and Handling of Study Data

The site PI is required to keep accurate records to ensure that the conduct of the study is fully documented, and to ensure that CRFs are completed for all subjects according to study guidelines outlined in the study protocol and the Data System Users Instruction Manual.

Access to the data entry screens will be user ID and password protected. Each user will be provided with a unique personal ID and password. The investigational site participating in this study will maintain the highest degree of confidentiality permitted for the clinical and research information obtained from the subjects in this clinical trial. Medical and research records should be maintained at each site in the strictest confidence. However, as part of the quality assurance and legal responsibilities of an investigation, the investigational site must permit authorized representatives of the sponsor(s) and health authorities to examine (and when required by applicable law, to copy) clinical records for the purpose of quality assurance reviews, audits, and evaluations of the study safety and progress. Unless required by the laws that permit copying of records, only the coded identity associated with documents or with other subject data may be copied (and all personally identifying information must be obscured). Authorized representatives as noted above are bound to maintain the strict confidentiality of medical and research information that is linked to identified individuals. The investigational site will normally be notified before auditing visits occur.

All data will be entered, stored, and managed in a relational database supported by database servers at the DCC. The results of all clinical and laboratory evaluations will be maintained in the subjects' medical records and the data will be transferred from these source documents directly to the electronic study CRFs. In order to maintain security, all data will be encrypted using the Secure Sockets Layer protocol. This protocol allows an encrypted link to be established between the DCC web server and the computer at each center. In addition, the data will be verified by a series of computerized edit checks, and all relevant data queries will be resolved regularly. All discrepancies will be reviewed, and any resulting queries will be resolved with the site personnel and amended in the database.

All changes made to CRFs will be recorded in an electronic audit trail to allow all data changes in the data system to be monitored and maintained in accordance with federal regulations. Once a CRF is entered into the database and the person entering the data indicates that CRF is complete, any change to that data will be entered into the system's audit trail. The audit trail will record the CRF and variable that is changed, the old value, the new value, the date and time the change was made, reason change was made, and the user ID of the person making the change. Once a change is completed, the data system will re-validate all variables on that CRF. The changed CRF will be required to pass all validity and logic consistency checks. If any edit

criteria fail, the system will generate appropriate queries. The clinical center coordinator will be asked to resolve the questions before the changes are completed.

The change system will allow certified DCC personnel and certified clinical center coordinators to make changes. Changes can be initiated by DCC monitors, DCC coordinators, and certified site personnel. Site personnel can access only the data for their own center. The system will generate weekly summary listings of all changes made to the database, the person making each change, and the reason for each change. These reports will be carefully reviewed by the DCC coordinator to monitor for unnecessary changes and/or problems with the data system.

## **13. ETHICAL CONSIDERATIONS AND COMPLIANCE WITH GOOD CLINICAL PRACTICE**

### **13.1 Statement of Compliance**

This clinical study will be conducted using cGCP, as delineated in *Guidance for Industry: E6 Good Clinical Practice Consolidated Guidance*, and according to the criteria specified in this study protocol. Before study initiation, the protocol and the informed consent documents will be reviewed and approved by an appropriate EC or IRB, and NIAID/NIDDK. Any amendments to the protocol or to the consent materials must also be approved by the IRB/EC and submitted to the applicable Health Authorities before they are implemented.

### **13.2 Informed Consent and Assent**

The informed consent form is a means of providing information about the trial to a prospective subject and allows for an informed decision about participation in the study. All subjects (or their legally acceptable representative) must read, sign, and date a consent form before entering the study, taking study drug, or undergoing any study-specific procedures. Consent materials for subjects who do not speak or read English must be translated into the subjects' appropriate language.

The informed consent form must be revised whenever important new safety information is available, whenever the protocol is amended, and/or whenever any new information becomes available that may affect participation in the trial.

A copy of the informed consent will be given to a prospective subject for review. The attending physician, in the presence of a witness if required by the IRB, will review the consent and answer questions. The prospective subject will be told that being in the trial is voluntary and that he or she may withdraw from the study at any time, for any reason.

### **13.3 Privacy and Confidentiality**

A subject's privacy and confidentiality will be respected throughout the study. Each subject will be assigned a sequential identification number, and these numbers rather than names will be used to collect, store, and report subject information.

## **14. PUBLICATION POLICY**

The CIT policy on the publication of study results will apply to this trial.

## Appendix 1. Schedule of Events for Extended Follow-up

Visit schedule based on anniversary of last islet transplant in CIT parent study; visit schedule repeats each year.	Timing	SC	Local Visits 			On-Site Visit
			3 month	6 month	9 month	Anniversary of Final Islet Transplant
	Visit #	0	See MOP for Table of Visit Numbers			
Visit Window (specified in days)		- 90	±14	±14	±14	± 30
GENERAL ASSESSMENTS						
Informed Consent		X				
Evaluate Inclusion/Exclusion Criteria		X				
Physical Exam		X 				X
AE /Hypoglycemic Events/Toxicity Assessment 		X 	X	X	X	X
Calculated GFR		X 				X
Insulin use		X 	X	X	X	X 
Urine pregnancy test (females)		X				
LOCAL LABORATORY ASSESSMENTS						
CBC (WBC + Diff & Plat) 		X 	X	X	X	X
Chemistry 		X 	X	X	X	X
Lipids 		X 				X
Alloantibody		Collect 3 months after immunosuppressive medication is stopped following graft failure.				
CENTRAL LABORATORY/METABOLIC ASSESSMENTS						
HbA1c 		X 				X
Fasting serum gluc/c-pep & serum creatinine 		X 				X
MMTT 		X 				X
CARDIOVASCULAR ASSESSMENTS						
Carotid intimal thickness (IMT)		Collect at 5 years post-initial-islet transplant visit in subjects who completed the baseline carotid IMT assessment in their CIT parent study. 				
IMMUNOSUPPRESSION LEVELS						
Blood Trough Levels (if applicable) 		X 	X	X	X	X
Visit schedule based on anniversary of last islet transplant in CIT parent study; visit schedule repeats each year.	Timing	SC	Local Visits 			On-Site Visit
			3 month	6 month	9 month	Anniversary of Final Islet Transplant
	Visit #	0	See MOP for Table of Visit Numbers			
Visit Window (specified in days)		- 90	±14	±14	±14	± 30
MECHANISTIC ASSAYS - University of Pennsylvania Sub-Study Only						
Autoantibody 				X		X
Immunophenotyping 				X		X
Cytokine profiling 				X		X
Glucose-potentiated arginine 						X
ARCHIVED SAMPLES						
Serum						X

---

 These visits are performed locally but can be done on site if preferred.

 Only collect if screening is  $\geq 90$  days since final parent study visit. Otherwise, results from final parent study visit should be used for screening (Visit 0).

 Also collect AE assessment at time of premature study termination, if applicable.

 Subjects must record insulin usage for 7 consecutive days within the visit window.

 Also collect as clinically indicated.

 Chemistry includes: Sodium, albumin, magnesium, chloride, potassium, alk phosphatase, total bilirubin, CO2, creatinine, ALT (SGPT), BUN, gamma GT, glucose, AST (SGOT), calcium, phosphorus

 Do not collect after confirmed graft failure.

 For those subjects who missed CIMT collection at the 5-year time point, collect at the next available opportunity.

 These visits are performed locally but can be done on site if preferred.

 Please refer to CIT07 Protocol Appendix 6 for details on the University of Pennsylvania Sub-Study.

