### 1.4.1.1 SIROLIMUS (RAPAMUNE®)

The FDA approved sirolimus (rapamycin, Rapamune®) as an immunosuppressive agent in 1999 (see product monograph for details). In 208 kidney transplant recipients receiving 5 mg of sirolimus daily compared to 124 receiving placebo, there was an increased incidence of hypercholesterolemia (46 vs. 23%), hyperlipemia (57 vs. 23%), rash (20 vs. 6%), arthralgia (31 vs. 18%), diarrhea (35 vs. 27%), anemia (33 vs. 21%), leucopenia (13 vs. 8%), thrombocytopenia (30 vs. 9%), and hypokalemia (17 vs. 9%). Side effects are related to drug concentration and are improved with maintenance of the sirolimus 24-hour trough level between 10–20 ng/mL.

Of infections, only mucosal herpes simplex virus (HSV) occurred at a greater rate with sirolimus. There was no increase in rate of malignancy (3.4 vs. 3.1%). While sirolimus was originally proposed as a non-nephrotoxic agent, it is becoming apparent that sirolimus-associated nephrotoxicity does occur in clinical practice. Crew *et al.* described two patients with thrombotic microangiopathy secondary to sirolimus exposure. Sirolimus alters the pharmacokinetic profiles of other CNIs (*e.g.*, tacrolimus) and may thereby potentiate nephrotoxicity. Fervenza *et al.* described nephrotoxicity from sirolimus in patients with chronic glomerulopathies that was non-reversible on cessation of therapy. Nephrotoxicity from combined sirolimus and tacrolimus has been described in patients with T1D undergoing islet transplantation, particularly where there is underlying pre-existing renal damage from diabetes.

The majority of islet transplant recipients receiving sirolimus in conjunction with tacrolimus have experienced transient mouth ulceration and lower extremity edema; perinephric edema and a high incidence of benign ovarian cysts have also been described in islet recipients in association with sirolimus. Pneumonitis and colitis have also occurred. The most common (> 30%) adverse reactions are: oral aphthous ulcers, peripheral edema, hypertriglyceridemia, hypertension, hypercholesterolemia, increased creatinine, abdominal pain, diarrhea, headache, fever, urinary tract infection, anemia, nausea, arthralgia, pain, and thrombocytopenia.

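### In CIT08, the central serum creatinine behind an annual renal endpoint stops at confirmed graft failure, and no other source is named for the analysis

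*Protocol*

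**What the plan says.** All references are to the CIT08 protocol unless CIT04 is named.

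Section 4.1.2 lists among the secondary endpoints "Serum creatinine and calculated eGFR at each annual study visit". It sets no condition on graft status and names no laboratory.

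Section 10.1.2 fixes the source of creatinine: "HbA1c and serum creatinine levels will be measured at central laboratories at study entry and at the annual follow-up visit". For eGFR it states only the equation: "GFR will be estimated using the updated CKD-EPI method". The planned summary is "Estimates of population means and confidence intervals for those means will be reported for each follow-up visit", with linear mixed models for the trend over time.

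Appendix 1 has one central creatinine collection, in the row "Fasting serum gluc/c-pep & serum creatinine". That row carries footnote 7, which reads "Do not collect after confirmed graft failure".

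Other parts of the same schedule carry no such stop. The local chemistry panel, whose listed contents include "creatinine, ALT (SGPT), BUN, gamma GT, glucose, AST (SGOT), calcium, phosphorus", is due at months 3, 6 and 9 and at the anniversary visit. The calculated GFR row is due at every anniversary visit. Section 7.2 ends only the metabolic assessments after confirmed graft failure and keeps the annual visit for safety. Section 8.2.1 keeps renal insufficiency among the adverse events to be recorded.

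**The concern.** Creatinine measures the kidney, not the graft, and it stays interpretable after the graft has failed. Bundling it with fasting glucose and C-peptide means that a stop written for graft-function tests also removes the central value on which section 10.1.2 relies.

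The loss is not random. It is triggered by graft failure, which is the event in the primary analysis (section 10.1.1) and which accumulates with follow-up. Annual means of central creatinine would therefore be taken over a set of subjects selected more strongly each year for graft survival, but labelled as estimates for the population.

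Renal function is of real interest in this cohort. Section 1.4.1.1 states: "Nephrotoxicity from combined sirolimus and tacrolimus has been described in patients with T1D undergoing islet transplantation". That sentence does not address the period after graft failure. It does show why a renal endpoint was chosen and why it should describe everyone who was exposed.

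**Working it through.** No formula or stated figure is involved, so the check sets the CIT08 provisions side by side and asks what is left at an annual visit after confirmed graft failure.

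| Renal data stream | Scheduled visits | Footnote 7? | After graft failure |
|---|---|---|---|
| Central creatinine (Appendix 1, shared row) | screening, anniversary | yes | stops |
| Local chemistry creatinine (Appendix 1) | screening, months 3, 6, 9, anniversary | no | continues |
| Calculated GFR (Appendix 1) | screening, anniversary | no | continues |
| Renal-insufficiency adverse events (section 8.2.1) | throughout | not applicable | continues |

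Three of the four streams continue. The one that stops is the one named in section 10.1.2.

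**Step 1, endpoint against schedule.** Section 4.1.2 wants creatinine and eGFR at each annual visit, and the local and calculated rows could supply both. The endpoint wording alone can be satisfied.

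**Step 2, analysis source against schedule.** Section 10.1.2 wants a central creatinine at the annual visit, and footnote 7 says not to collect it after failure. Both cannot be followed. The GFR sentence names no laboratory, so the source of the creatinine behind the calculated GFR after failure is left open.

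**Step 3, effect on the summaries.** If only central values are used, the mean at a given year runs over subjects without confirmed failure. The mixed model does better, because values from before failure still enter it. It has no central observation after failure, however, and must extrapolate from the course before failure. Section 7.2 foresees that some subjects stop immunosuppression after failure, so that course may change. The documents do not show in which direction, so no sign of bias can be claimed.

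**Step 4, number affected.** With N enrolled and a fraction f failed by a given year, N × f subjects lack a central creatinine. N is about 75 (synopsis); f is not given. Purely as an assumption, f of 20% to 40% would give 0.20 × 75 = 15 to 0.40 × 75 = 30. Those subjects would still be due an annual local creatinine.

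**Step 5, why switching laboratory at failure does not work.** Let F = 1 at visits after failure and L = 1 when the value is local. If local values are used only after failure, L = F for every observation. A laboratory covariate and a change after failure are then the same column in the model, and neither can be estimated apart from the other. Under one laboratory throughout, L is constant and the effect of failure is not mixed with the assay.

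**Step 6, sign of a bundling slip.** The CIT04 reduced follow-up schedule (CIT04 Appendix 5), which applies after study treatment is discontinued, keeps a central serum creatinine at 1 and 2 years after the initial transplant. CIT08 lists no C-peptide-to-creatinine ratio among its endpoints, so nothing in section 4.1.2 ties creatinine to the graft tests.

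**The case against.** The strongest reply is that no renal information is lost. Local creatinine is due four times a year, calculated GFR is due annually without the footnote, and renal insufficiency is recorded for all subjects. The endpoint itself names no laboratory, and the eGFR sentence names none either. On this view one clause of section 10.1.2 is loosely worded, and the choice of laboratory can be left to the SAP.

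Much of that stands. A reader might infer from footnote 7 that nephrotoxicity would be reported only for subjects whose grafts still work. The documents do not support this: three renal streams run on after failure, nothing bars the local values from the analysis, and values from before failure still inform the trend. A reader might also infer that both creatinine and eGFR are tied to the central value; only creatinine is.

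What does not stand is that the conflict therefore disappears. Section 10.1.2 names a source, and no provision authorises another after failure. One analyst would drop visits after failure and another would fill them with local values, giving different populations and different assays under one endpoint label. An SAP can choose between them, but it cannot recover central samples that were never drawn.

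It could also be said that creatinine counts as metabolic, because its row sits under a heading that joins central laboratory and metabolic assessments. That would explain the footnote. It would not remove the conflict with section 10.1.2.

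**Conclusion.** The point holds as a contradiction about the data source, not as a loss of renal safety follow-up. Section 10.1.2 requires an annual central creatinine; Appendix 1 stops it at confirmed graft failure; no substitute is specified for the endpoint or for the creatinine behind eGFR. Followed literally, the annual central creatinine means describe subjects with functioning grafts, with missingness triggered by the primary event.

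This rests on two readings: that footnote 7 applies to the whole shared row, as printed, and that the central-laboratory sentence is meant as the source for the analysis. Neither the size of the effect nor its direction can be derived from the documents. The matter is worth correcting because the inconsistency touches a stated endpoint and the remedy is small.

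**What to change.** Choose one source for all visits and write it into both places.

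- **Preferred:** split serum creatinine from the shared central row in Appendix 1 and remove footnote 7 from it, so that the central value continues at annual visits after failure. State that this value also feeds the CKD-EPI eGFR.
- **Alternative:** amend section 10.1.2 so that the annual local chemistry creatinine, already scheduled for every subject before and after failure, supplies creatinine and eGFR at all visits. Report a local-versus-central comparison on the visits that have both.

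Do not change laboratory only at graft failure and adjust with a laboratory covariate, for the reason in step 5 of the working. Report renal results for all subjects and by graft status.

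The first option costs one extra central creatinine sample per subject per year after failure. The second needs no new sample but relies on local assays. Both need a short protocol amendment. The same amendment should settle HbA1c, which has the same conflict between section 10.1.2 and footnote 7 and has no local substitute in the schedule.
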